4.2.7.4 EQ-5D-5L

The following summaries will be presented by treatment.

- The distribution of responses for each of the 5 dimensions assessed at each visit
- The shift table presenting baseline and last observation post-baseline value by dimension.
- The change from baseline on the visual analogue scale will also be evaluated by treatment group.

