Adolescents within the European Union (EU) will continue to receive only the Q8W dosing regimen as per the predecessor study. In order to maintain the blind of the predecessor study, this group will receive injections every 4 weeks for the first 3 doses (active drug at Visits 1 and 3, placebo administered at Visit 2) followed by every 8 weeks thereafter.

Adolescents previously assigned to the placebo arm in the predecessor study

¹ For the purposes of this study the European Union (EU) is defined as consisting of the following countries: Bulgaria, Czech Republic, France, Germany, Italy, Poland, Romania, Spain, Sweden and the United Kingdom.

Adolescents within the EU who were randomized to placebo in the predecessor study will be assigned to benralizumab 30 mg Q8W in this study (every 4 weeks for the first 3 doses followed by every 8 weeks thereafter).

After the first 3 doses, adolescent patients within the EU will be receiving open-label treatment with IP administered at their bimonthly visit; however, they will still follow an every 4 weeks study visit schedule (see Table of Assessments, [Table 2](#)).

Target patient population

Patients who complete Study D3250C00017, D3250C00018, or D3250C00020 on investigational product may be eligible for this study.

Investigational product and mode of administration

Benralizumab 30 mg/mL solution for injection in an accessorized pre-filled syringe (APFS) OR matching placebo in an APFS will be administered SC at the study site according to the dosing regimens described below.

Dosage

Refer to Study Design section above.

Duration of treatment

Adults: This is a 68-week study with the last dose of study drug administered at Week 52. An end of treatment (EOT) visit will be conducted at Week 56. A final follow-up visit will be conducted at Week 68, which is 16 weeks after the last dose of study drug.

The total planned study duration is 68 weeks.

Adolescents: This is a 120-week study with the last dose of study drug administered at Week 104. An EOT visit will be conducted at Week 108. A final follow-up visit will be conducted at Week 120, which is 16 weeks after the last dose of study drug.

The total planned study duration is 120 weeks.

Statistical methods

All safety and efficacy parameters will be analyzed descriptively based on the full analysis set. The full analysis set includes all randomized patients who received any dose of IP.

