5.3.2.4 EQ-5D-5L

The EQ-5D-5L questionnaire assesses 5 dimensions: mobility, self-care, usual activities, pain/discomfort, and anxiety/depression. Each dimension has 5 response options (no problems, slight problems, moderate problems, severe problems, and extreme problems) that reflect increasing levels of difficulty.

The patient will be asked to indicate his/her current health state by selecting the most appropriate level in each of the 5 dimensions. The questionnaire also includes a visual analogue scale, where the patient will be asked to rate current health status on a scale of 0-100, with 0 being the worst imaginable health state

The EQ-5D-5L will be completed at every scheduled visit.

The Investigator/authorized delegate will check patient adherence to the EQ-5D-5L at every scheduled visit as shown in [Table 1](#) or [Table 2](#).

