8.4 Variables for analyses

8.4.1 Calculation or derivation of efficacy variables

All efficacy objectives will be evaluated for the treatment period, defined as the period after administration of IP at Visit 1 to the conclusion of the EOT visit, inclusive.

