8. APPENDICES

8.1 Appendix A Analysis visit windows

Table 2 Adjusted visit windows for variables with scheduled visits every 4 weeks (eg, EQ-5D-5L)

| Analysis Visit | Scheduled study day | Adjusted visit window |
|--------------------------|---------------------|----------------------------------|
| Week 0 | 1 | Study Day \leq 1 |
| Week 4 | 29 | 2 \leq Study Days \leq 42 |
| Week 8 | 57 | 43 \leq Study Days \leq 70 |
| Week 12 | 85 | 71 \leq Study Days \leq 98 |
| Week 16 | 113 | 99 \leq Study Days \leq 126 |
| Week 20 | 141 | 127 \leq Study Days \leq 154 |
| Week 24 | 169 | 155 \leq Study Days \leq 182 |
| Week 28 | 197 | 183 \leq Study Days \leq 210 |
| Week 32 | 225 | 211 \leq Study Days \leq 238 |
| Week 36 | 253 | 239 \leq Study Days \leq 266 |
| Week 40 | 281 | 267 \leq Study Days \leq 294 |
| Week 44 | 309 | 295 \leq Study Days \leq 322 |
| Week 48 | 337 | 323 \leq Study Days \leq 350 |
| Week 52 | 365 | 351 \leq Study Days \leq 378 |
| Week 56 (EOT for adults) | 393 | 379 \leq Study Days \leq 406 |
| Week 68# (FU for adults) | 477 | 407 \leq Study Days |
| Week 60* | 421 | 407 \leq Study Days \leq 434 |
| Week 64* | 449 | 435 \leq Study Days \leq 462 |
| Week 68* | 477 | 463 \leq Study Days \leq 490 |
| Week 72* | 505 | 491 \leq Study Days \leq 518 |
| Week 76* | 533 | 519 \leq Study Days \leq 546 |
| Week 80* | 561 | 547 \leq Study Days \leq 574 |
| Week 84* | 589 | 575 \leq Study Days \leq 602 |
| Week 88* | 617 | 603 \leq Study Days \leq 630 |
| Week 92* | 645 | 631 \leq Study Days \leq 658 |
| Week 96* | 673 | 659 \leq Study Days \leq 686 |
| Week 100* | 701 | 687 \leq Study Days \leq 714 |

Table 2 Adjusted visit windows for variables with scheduled visits every 4 weeks (eg, EQ-5D-5L)

| Analysis Visit | Scheduled study day | Adjusted visit window |
|---------------------------------|---------------------|-----------------------|
| Week 104* | 729 | 715≤Study Days≤742 |
| Week 108* (EOT for adolescents) | 757 | 743≤Study Days≤770 |
| Week 120* (FU for adolescents) | 841 | 771≤Study Days |

Visit for adults only.

* Visits for adolescents only.

Table 3 Adjusted visit windows for variables with scheduled every 12 weeks visits (eg, ACQ-6 and AQLQ(S)+12)

| Analysis Visit | Scheduled study day | Adjusted visit window |
|---------------------------------|---------------------|-----------------------|
| Week 0 | 1 | Study Day≤1 |
| Week 12 | 85 | 2≤Study Days≤126 |
| Week 24 | 169 | 127≤Study Days≤210 |
| Week 36 | 253 | 211≤Study Days≤294 |

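### The EQ-5D-5L dimension shift table takes the last post-baseline value, so it mixes off-treatment Week 68 values with on-treatment values

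*SAP*

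**What the plan says.** SAP 4.2.7.4 lists three EQ-5D-5L summaries: response distributions for each dimension at each visit, change on the visual analogue scale (VAS), and "The shift table presenting baseline and last observation post-baseline value by dimension". The last carries no limit to EOT or to the on-treatment period.

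Protocol 5.3.2.4 sets the collection rule: "The EQ-5D-5L will be completed at every scheduled visit". SAP Appendix A, Table 2, which names EQ-5D-5L as its example variable, has a row "Week 68# (FU for adults) | 477", with a window from Day 407 onwards. SAP 2.3 uses all data for analyses not tied to a visit unless otherwise stated, and SAP 4.1 uses all data captured in the study for secondary endpoints. Nothing therefore narrows the word last.

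Protocol 8.4.1 states "All efficacy objectives will be evaluated for the treatment period" and ends that period with the EOT visit. Protocol 8.5.1 lists EQ-5D-5L among the efficacy endpoints. SAP Section 6 records no change from the protocol.

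**The concern.** A shift table pairs each patient's baseline category with a later one. It can be interpreted only if the later value describes a known state. Here the state depends on whether the patient attended follow-up. One cell can hold adults still within the treatment period and adults who have been off injections for months. In the combined adult and adolescent table, mostly off-treatment adults are also pooled with adolescents restricted to on-treatment data.

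A reader who takes the table as the status at the end of treatment would be reading something else, and could not separate a change on treatment from one after withdrawal. Other parts of the SAP keep these apart. The physical examination shift runs from baseline to EOT (4.2.5.3), ACQ-6 and AQLQ(S)+12 responder status is anchored at EOT (3.3.1, 3.3.2), and exacerbations and healthcare use are split into on-treatment, post-treatment and on-study periods (3.2.1.1, 3.4).

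**Working it through.** **Inputs.** The protocol synopsis (duration of treatment, adults) fixes the last dose: "This is a 68-week study with the last dose of study drug administered at Week 52". It puts EOT four weeks later, in Week 56, and for the final visit it says "A final follow-up visit will be conducted at Week 68, which is 16 weeks after the last dose of study drug". SAP 2.3 counts the first-dose day as Day 1, so scheduled study day = 7 × week + 1. SAP 3.1.1 caps the on-treatment period at last dose + 28 + 7 days when the EOT or IPD visit is late.

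**Reproducing the plan's figures.**
- Last dose to follow-up: 68 − 52 = 16 weeks, as the protocol states.
- Week 52: 7 × 52 + 1 = Day 365. Week 56: 7 × 56 + 1 = Day 393. Week 68: 7 × 68 + 1 = Day 477. All three match SAP Table 2.

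**Distance of the value used from EOT.**
- EOT is 56 − 52 = 4 weeks after the last dose.
- Follow-up is 68 − 56 = 12 weeks after EOT, or 477 − 393 = 84 days.
- The on-treatment cap falls on Day 365 + 35 = Day 400, so follow-up is 477 − 400 = 77 days beyond it. With a ±7-day visit window (Days 470 to 484), the earliest in-window follow-up is still 70 days beyond it.
- Adults re-randomised from placebo to Q8W have active injections at Weeks 0, 4, 8 and 16, then every 8 weeks (protocol 4.2.3.1). This gives Week 48 as active and Week 52 as placebo, so Week 68 is 68 − 48 = 20 weeks after their last active injection.

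**Value each patient contributes in the adult completion analysis.**

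| Patient | Last post-baseline EQ-5D-5L | State |
|---|---|---|
| Adult in BORA, follow-up value present | Week 68, Day 477 | 16 weeks after last dose |
| Adult completing treatment, no follow-up value | EOT, Day 393 | 4 weeks after last dose |
| Adult stopping early, returns for follow-up | Follow-up visit | 16 weeks after last dose (protocol 3.6) |
| Adult stopping early, IPD visit only | IPD | About 4 weeks after last dose |
| Adolescent | Week 56 or IPD (SAP 4.1.1) | On-treatment data only |

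Patients moving to MELTEMI leave BORA at their EOT visit and are summarised separately, so they are outside this table's problem.

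The same wording would select the Week 120 value for adolescents in the later addendum: Day 841 against Day 757 at EOT, again 84 days.

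**The case against.** The strongest objection is that follow-up data belong to the stated objective. The protocol's quality-of-life objective (Section 2), with EQ-5D-5L as an endpoint, covers the 16 weeks after the last dose as well as treatment, and SAP 1.1 repeats it. The protocol is thus in tension with itself, and a table reaching Week 68 is not improper in principle. SAP 4.2.5.4 also uses the last post-baseline observation for the ECG shift. This stands. It supports showing a shift to follow-up, but not a single table in which attendance decides the state each patient represents.

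Several stronger readings are tempting, and the documents do not support them:
- A reader might infer that the protocol's EQ-5D-5L outcome at EOT is undermined. Protocol 8.4.3.4 and 8.5.1.4 set that outcome for the VAS only, which the SAP analyses separately. For the dimensions they ask for by-visit distributions, which the SAP provides.
- A reader might infer that no other summary reaches from baseline to the end of treatment. The by-visit distributions have separate Week 0, Week 56 and Week 68 windows, so group-level change is visible. What is missing is the patient-level pairing at EOT.
- A reader might infer that a rebound after stopping is presented as the treatment result. The SAP does not label the table as an EOT result, and neither document shows that a rebound occurs.
- A reader might infer that every adult completer is affected. SAP 4.2.1 also counts MELTEMI patients as completers, and they have no BORA follow-up.

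The pooling of age groups is partly mitigated, because SAP 4.1.1 also presents adults and adolescents separately. The adult-only table still mixes states.

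**Conclusion.** The point holds for this one table. As worded, it uses a value 12 weeks after EOT and 16 weeks after the last dose for adults who stay in BORA and have a follow-up EQ-5D-5L, and an EOT or IPD value for those who do not. It is the only paired patient-level view of the five dimensions that the SAP plans. It conflicts with protocol 8.4.1 read with 8.5.1, and SAP Section 6 does not declare the departure.

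The consequence is limited to interpretation. The study is descriptive and not powered for any test, so no error rate or sample size is involved, and the by-visit distributions and VAS analysis are untouched. How many patients fall into each state depends on follow-up attendance, which the documents do not give.

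The conclusion assumes that the wording is applied literally. The bullet does not name Week 68; that follows from the collection schedule and from the general all-data rules in SAP 2.3 and 4.1.

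**What to change.** In SAP 4.2.7.4, define the dimension shift as baseline versus last on-treatment observation (EOT or IPD, within the on-treatment period of SAP 3.1.1). Add a separately labelled shift to the follow-up visit, so that the follow-up part of the objective is still covered. The SAP already applies the 3.1.1 periods to exacerbations and healthcare use, so no new definition is needed.

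If the sponsor prefers to keep the last observation of any kind, SAP Section 6 should record the departure from protocol 8.4.1 and the table title should say that follow-up values are included. That would settle the conflict but not the mixing.

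The cost is one changed phrase, one data filter and one additional descriptive table. No new data are needed.

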4.2.8 Analysis methods for healthcare resource utilisation

The number and percentage of patients with asthma specific resource utilisation (defined in Section 3.4) will be presented by treatment group. In addition, the annual rate of healthcare resource utilisation will be summarised by treatment group for the patients from SIROCCO and CALIMA with predecessor baseline blood eosinophil count $\geq 300/\mu\text{L}$ and $< 300/\mu\text{L}$. Data from ZONDA will be summarised for the FAS regardless of predecessor baseline eosinophil counts.

4.2.9 Analysis methods for pharmacokinetic variables

The PK analyses will be performed at or under the guidance of AstraZeneca Research and Development. Benralizumab serum concentrations will be summarised using descriptive statistics at each visit by treatment group using PK analysis set.

4.2.10 Analysis method for immunogenicity variables

Demographic and patient characteristics including age, sex, race, ethnicity group and BMI subgroups ($\leq 35 \text{ kg/m}^2$, $> 35 \text{ kg/m}^2$) by ADA status (positive, negative) and ADA positive subgroups (stable persistently positive, nAb positive) will be presented by treatment group.

The number and percentage of patients within each ADA response category defined in Section 3.6 will be summarised by treatment group and ADA status in predecessor studies. Anti-drug antibody response and the corresponding titre will be summarised by visits. In addition, the ADA response will be presented cumulatively by visit. A summary of ADA titres over time by ADA status (ADA positive patients at any visit, ADA newly persistently positive, ADA stable persistent positive, and nAb positive patients) will be provided to monitor titre changes over time.

Newly persistently positive ADA response and ADA stable persistently positive by maximum titer quartile subgroups will be presented by treatment group. A table will be presented to list patients in each treatment group with treatment boosted ADA, and repeated for those patients with maximum titer above the 3rd quartile. For each patient, the table will list the titre at study baseline, maximum titre, and the fold-change that is above the 3rd quartile of the maximum titre from baseline. Similar summaries will be provided for patients with decrease in titre

including the baseline titre, maximum titre, post maximum titre that is decreased >75% from the maximum titre, and its percent reduction from the maximum titre.

The relationship among the following parameters with ADA status (positive, negative) and ADA positive subgroups (ADA titre greater than median of the maximum, newly persistently positive, stable persistently positive, nAb positive) will be presented, unless stated otherwise.

- The annual exacerbation rate during on-study period, on-treatment period and post-treatment period
- Change from baseline in pre-BD FEV₁ for each post-baseline visit
- Adverse events (AEs) and serious adverse events (SAEs) by System Organ Class (SOC) and Preferred Term (PT), AEs and SAEs by preferred term, AEs and SAEs by PT and causality, and hypersensitivity events by PT and causality. These summaries will be conducted during on-treatment period. Additional AE summaries may be added as needed, based on review of the pre-specified summaries
- Absolute blood eosinophil counts (cells/ μ L) for each visit
- Benralizumab serum concentrations for each visit

The following plots will be provided:

- Percentage of Anti-Drug Antibody positive patients by visit
- Anti-Drug antibody titres by visit
- Median blood eosinophil counts profile by (1) treatment groups and ADA subgroup (ADA positive and ADA negative), and (2) by ADA subgroups (ADA positive, ADA negative, newly persistently ADA positive, stable persistently ADA positive, ADA with titer > median of maximum titre, ADA with titer > 3rd quartile of maximum titre) for each treatment group.

Note data from adolescents will not be plotted for the median blood eosinophil counts.

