3.1.1 Adverse events

Adverse event (AE) and serious adverse event (SAE) are defined in Section 7.1 of the CSP. All AEs, including SAEs, will be collected from the time the patient signs the informed consent throughout the treatment period and including the follow-up period (Visit 16, Week 68 for adults, and Visit 29, Week 120 for adolescents). Any AEs that are unresolved at follow-up in the study will be followed up by the Investigator for as long as medically indicated, but without further recording in the CRF. If the record was entered in CRF for an ongoing event post-study follow-up visit, study output will list those events and indicates as such.

Adverse events experienced by the patients will be collected throughout the entire study and will be coded by the AstraZeneca designee using the latest version of the Medical Dictionary for Regulatory Activities (MedDRA).

Adverse event data will be categorised according to their onset date into the following study periods:

- AEs in the on-study period are defined as those with onset between the day of first dose of study treatment and the day of the scheduled follow-up visit, inclusive.
- AEs in the on-treatment period are defined as those with onset between the day of the first dose of study treatment and scheduled EOT for patients who complete study treatment or scheduled IPD visit for those patients who prematurely discontinue study treatment, inclusive. If the EOT or IPD visit is beyond the protocol defined visit window, AEs with onset after the day of last dose of study treatment date + 28 days + 7 days (visit window) will be excluded from the on-treatment period and instead assigned to the post-treatment period.
- AEs in the post-treatment period are defined as those with onset after an on-treatment period defined above.

For instances where a patient attends the safety follow-up visit only, but does not attend an earlier IPD visit or EOT visit, adverse events occurring on or after the day of the first dose of study treatment and on or before the last dose of study medication + 28 days will be assigned to the on-treatment period, while AEs with onset date after this time will be assigned to the post-treatment period.

For adolescent data included in the adult completion analyses, only on-treatment AEs will be summarised. AEs will be categorised as having occurred in the on-treatment period if they satisfy one of the following conditions.

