3.6 Immunogenicity variables

ADA assessments will be conducted utilising a tiered approach (screen, confirm, titre). The presence of neutralising antibodies (nAb) will be tested in all ADA-positive samples using a ligand binding assay.

For each patient, the following response variables will be evaluated based on ADA status in predecessor studies and data from the start of the BORA through to the BORA FU visit (Week 68 for adults and Week 120 for adolescents). For adolescents in adult completion analysis phase, the responses variables will be evaluated from the start of the BORA through the Week 56 visit or IPD visit, whichever is earlier.

- ADA positive at any visit (including baseline, post-baseline, unscheduled visits)
- ADA positive at both baseline and at least one post-baseline
- ADA positive at baseline only
- ADA positive at post-baseline only
- ADA newly persistently positive: defined as ADA negative at BORA baseline and at least 2 post-baseline ADA positive measurements with at least 16 weeks (112 days) between the first and last positive measurement, or an ADA positive result at the last available assessment.
- ADA stable persistently positive: defined as ADA positive at BORA baseline and at least 2 post-baseline ADA positive measurements with at least 16 weeks (112 days) between the first and last positive measurement.

- ADA transiently positive: defined as having at least one post-baseline ADA positive measurement and not fulfilling the conditions for either newly or stable persistently positive.
- nAb positive
- Newly treatment-induced ADA positive: defined for patients who in predecessor study were not ADA positive any time, but post-baseline in the current study is ADA positive for the first time.
- Decrease in titre: defined as having at least two post-baseline ADA positive results, and a >75% decrease from the maximum post-baseline titre which must be maintained from the time when it first occurred until the last on-treatment period visit. The >75% decrease can include going from a positive to negative titre result (e.g. a change of titer from ≥ 200 to negative).
- Treatment boosted ADA: at least one of patient's post baseline titres is > 4-fold of the baseline titre.

Treatment-emergent ADA positive (BORA-specific incidence) is defined as either newly treatment-induced ADA positive or treatment boosted ADA as defined above.

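### ADA status in the SAP 4.2.10 event tables can be set by samples taken after the event, which mainly dilutes any real link between ADA and hypersensitivity or loss of efficacy

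*SAP*

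**What the plan says.** SAP 3.6 evaluates each patient's ADA response categories on predecessor-study status and on "data from the start of the BORA through to the BORA FU visit (Week 68 for adults and Week 120 for adolescents". The first category is "ADA positive at any visit (including baseline, post-baseline, unscheduled visits". A patient negative at BORA baseline also counts as newly persistently positive on the strength of "or an ADA positive result at the last available assessment", and that assessment may be the follow-up visit.

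SAP 4.2.10 then presents "The relationship among the following parameters with ADA status (positive, negative) and ADA positive subgroups". The parameters include the annual exacerbation rate (on-study, on-treatment and post-treatment) and tables of AEs, SAEs and hypersensitivity events. Of the AE tables it says: "These summaries will be conducted during on-treatment period". Under SAP 3.1.1 that period covers AEs "with onset between the day of the first dose of study treatment and scheduled EOT for patients who complete study treatment", or up to the IPD visit for those who stop early. For adults, EOT is Week 56.

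The binary status is not defined in 4.2.10. The nearest wording there belongs to the titre-over-time summary, which lists "ADA status (ADA positive patients at any visit, ADA newly persistently positive, ADA stable persistent positive, and nAb positive patients".

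One exception is written in: for adolescents in the adult completion analysis, SAP 3.6 ends the ADA window at Week 56 or IPD, whichever is earlier.

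**The concern.** On the any-visit reading, each patient carries one ADA label based on the whole record, and that label sorts events that may have happened months before the first positive sample. An adult whose on-treatment samples were all negative, and who is first positive at Week 68, has every on-treatment event tabulated as ADA positive. Nothing in SAP 3.6 or 4.2.10 orders an event against the first positive sample. The cumulative ADA display by visit is not linked to events.

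Protocol 1.4 names reduced efficacy and hypersensitivity as the theoretical risks of ADA, and these tables are where the SAP looks for both. Patients who had placebo in the predecessor study start benralizumab at Visit 1, so their first exposure falls inside BORA. For them the order of conversion and event is central.

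**Working it through.** The documents give no ADA incidence and no event rate by ADA status, so there is no figure of the plan's own to reproduce.

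**1. Time before the first positive sample.** Inputs: adult ADA analysis visits at Weeks 0, 8, 16, 28, 44, 52, 56 and 68 (SAP Table 7) and a 56-week on-treatment period. For a first positive at week w, the share of on-treatment time that precedes it is f = min(w, 56)/56.

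| First positive | f |
|---|---|
| Week 0 | 0% |
| Week 8 | 14% |
| Week 16 | 29% |
| Week 28 | 50% |
| Week 44 | 79% |
| Week 52 | 93% |
| Week 56 or 68 | 100% |

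If the first positive were equally likely at each post-baseline visit (an assumption), the mean is (8 + 16 + 28 + 44 + 52 + 56 + 56)/(7 × 56) = 260/392 = 66%. Without Week 68 it is 204/336 = 61%. Both figures describe new converters only.

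**2. Dilution.** Suppose the event rate is at the reference level before conversion and RR times that afterwards, and take the first positive sample as the conversion date. A converter's whole-period rate ratio is then f + (1 − f) × RR.

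- Week 28, RR 3: 0.50 + 0.50 × 3 = 2.0
- Week 44, RR 3: 0.786 + 0.214 × 3 = 1.43
- Week 8, RR 3: 0.143 + 0.857 × 3 = 2.71

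A simulation averages over conversion times. Its assumptions are 5% to 20% conversion by Week 68 at constant hazard, 10% discontinuation, 0.05 events per patient-year and nobody positive at baseline. True ratios of 1, 2, 3 and 5 appear in the ever-positive table as about 1.0, 1.4, 1.8–1.9 and 2.6–2.7. Splitting person-time at the simulated conversion time returns about 1, 2, 3 and 5. About 15–16% of ever-positive patients are first detected at the Week 68 sample.

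**3. Association when there is no effect.** Patients who leave early give fewer samples and less AE time, which can tilt patient percentages. Assume 12% conversion by Week 56 and 1.5 AEs per patient-year.

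- 20% dropout, no baseline positives, no samples after dropout: 79.0% against 73.3%, ratio 1.08.
- 20% dropout, 6% baseline positives, IPD and follow-up samples for discontinuers: 75.4% against 73.3%, ratio 1.03.
- As the second case with 10% dropout: ratio 1.02.

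The share of first AEs in the positive column that precede the first positive sample is about 75% in the first case and about 52% in the second, so it depends heavily on how many patients are positive at baseline.

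**4. What a split at the first positive sample still misses.** The adult on-treatment sampling intervals are 8, 8, 12, 16, 8 and 4 weeks. With conversion uniform over time, the post-conversion time still labelled negative is the sum of squared intervals over 56²: (64 + 64 + 144 + 256 + 64 + 16)/3136 = 608/3136 = 19%.

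**The case against.** Five counter-arguments deserve weight.

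- **The status is inferred.** The any-visit wording in 4.2.10 sits with the titre summary, and the SAP's amendment history refers to a global ADA analysis plan that is not among these documents. This stands. But no other definition is given, and if another rule is intended the SAP should state it.
- **A reader might infer that the tables would manufacture an ADA–AE association.** The documents do not support that. The ratio under no effect is close to 1 and rests on assumed rates. Transfer to MELTEMI, a planned source of short follow-up, is summarised separately under SAP 2.1. Exacerbation rates already use person-time, and the post-treatment rates carry little look-ahead.
- **A reader might take the Week 68 problem to apply to everyone in the positive column.** It does not. Baseline positives are correctly timed, and adolescent status in the adult completion analysis stops at Week 56 or IPD. For adolescents who convert, the look-ahead within treatment remains.
- **The study is descriptive and 4.2.10 allows further AE summaries.** Both are true, so type I error is not at issue. But any further summary is to follow review of the planned tables, and a diluted signal may not prompt one.
- **A time split has its own faults.** It mislabels some post-conversion time, and it needs a rule for reactions sampled on the day, since Protocol 6.9 asks for an ADA sample during an acute reaction. This stands and shapes the fix.

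**Conclusion.** The point holds for patients ADA negative at BORA baseline who become positive later, on the only definition of status that the SAP text supports. Its main effect is to pull a real ADA association with hypersensitivity or exacerbations towards 1. By arithmetic from the SAP's own visit schedule, a ratio of 3 becomes 2.0 at Week 28 and 1.43 at Week 44. The size in the full positive column depends on the mix of baseline positives and conversion times, which the documents do not give. A spurious difference in the AE percentages is a secondary matter, at a ratio of about 1.02 to 1.08 under the stated assumptions. The planned tables need a time-ordered companion; they need not be withdrawn.

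**What to change.** In SAP 4.2.10:

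1. Define the binary ADA status used in the event tables, including its sampling window.
2. Keep the planned tables and label them as whole-record classifications. Footnote the persistence and maximum-titre subgroups in the same way, because a time split does not change them.
3. Add a time-ordered summary for AEs, SAEs, hypersensitivity events and exacerbations. Patients positive at BORA baseline count as positive from Day 1. All others contribute events and person-time as negative before the first positive sample and as positive from that date. Report rates per 100 patient-years, as SAP 4.2.5.1 already does for AEs, and annual rates for exacerbations.
4. State that an event whose own same-day sample is the first positive counts as ADA positive.
5. For each hypersensitivity case, list the onset date, the last negative sample date and the first positive sample date.

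The cost is SAP wording, one derived date per patient for the summary, and a short listing; no new data are collected. The downside to state is that conversion is known only to the sampling interval, up to 16 weeks (Week 28 to Week 44), so some post-conversion time will be labelled negative.
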